## 6.2. Definition of Populations

Analysis populations are defined in [Table JAIM.6.2](#) along with their associated purpose. The treatment groups and inferential comparisons described in this table will be used unless otherwise specified. Also, unless otherwise specified, patients will be analyzed according to the treatment to which they were assigned. Patients who are randomized to 4 mg, but who have decreased renal function, identified by an eGFR measurement of  $<60 \text{ mL}/\text{min}/1.73\text{m}^2$ , will receive a dose of 2 mg QD. These patients will be summarized within the 4-mg treatment arm for all summaries unless otherwise noted. A listing of treatment assignments showing the randomized treatment vs the treatment received for subjects with low eGFR ( $<60 \text{ mL}/\text{min}/1.73\text{m}^2$ ) will be provided. Maximized extended enrollment (ME2) patients in Study JAHZ will be enrolled in China to meet country-level regulatory requirements and these patients will be excluded from all analyses in Study JAIM, unless otherwise noted. [Appendix 3](#) describes the analyses for all patients from China sites including the ME2 cohort.

Due to the confirmed misconduct at **PPD** that is likely to have significant impact on reliability and robustness of data at this particular site, the patients from this site will be excluded from the modified intent to treat (mITT) population and safety population.

**Table JAIM.6.2. Analysis Populations**

Population	Description
Entered Population	
Definition: All patients who signed informed consent form in Study JAIM
 
Purpose: Used for patient allocation summary
 
Treatment Groups: As given in Table JAIM.6.1

Randomized Population	
Definition: All patients who were randomized/assigned in Study JAIM (Note: patients randomized to active treatment during the originating study will be assigned to the same, blinded dose of baricitinib in Study JAIM; patients randomized to placebo during the originating studies will be randomized 1:1 to blinded baricitinib treatment of 2 mg once daily (QD) or 4 mg QD in Study JAIM)
 
Purpose: Used for patient allocation summary
 
Treatment Groups: As given in Table JAIM.6.1

Modified Intent-to-Treat (mITT) Population	
Definition: All participating patients, excluding those from PPD, who receive at least 1 dose of study treatment in Study JAIM (regardless if the patient does not receive the correct treatment, or otherwise does not follow the protocol)
 
Purpose: Used for efficacy and health outcomes related analyses
 
Treatment Groups: As given in Table JAIM.6.1

Safety Population	
Definition: For the purpose of analysis of Study JAIM alone, the safety population is defined as all patients, excluding those from PPD, who receive at least 1 dose of investigational product in Study JAIM and who did not discontinue from the study for the reason 'Lost to Follow-up' at the first postbaseline visit
 
Purpose: Used for safety analyses
 
Treatment Groups: Safety analyses will be analyzed according to 5 treatment groups as defined in Table JAIM.6.1

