If a patient's investigational product is discontinued as a result of an AE, study site personnel must report this to Lilly or its designee via eCRF, clarifying if possible, the circumstances leading to any dosage modifications, or discontinuations of treatment.

9.2.1. *Serious Adverse Events*

An SAE is any AE from this study that results in one of the following outcomes:

- Death
- Initial or prolonged inpatient hospitalization
- A life-threatening experience (that is, immediate risk of dying)
- Persistent or significant disability/incapacity
- Congenital anomaly/birth defect
- Important medical events that may not be immediately life-threatening or result in death or hospitalization, but may jeopardize the patient or may require intervention to prevent one of the other outcomes listed in the definition above.

All AEs occurring after signing the ICF are recorded in the eCRF and assessed for serious criteria. The SAE reporting to the sponsor begins after the patient has signed the ICF and has received investigational product. However, if an SAE occurs after signing the ICF, but prior to receiving investigational product, the SAE should be reported to the sponsor according to SAE-reporting requirements and timelines, if it is considered reasonably possibly related to study procedure.

Study site personnel must alert Lilly or its designee of any SAE within 24 hours of investigator awareness of the event via a paper SAE form. If alerts are issued via telephone, they are to be immediately followed with official notification on study-specific SAE forms. The SAE form should be completed by the investigator, and submitted via fax to the sponsor's global patient safety department. This form includes a fax cover page that is pre-populated with the appropriate fax number. The 24-hour notification requirement refers to the initial SAE information and all follow-up SAE information. Patients with a serious hepatic AE should have additional data collected using the eCRF.

Pregnancy (during maternal or paternal exposure to investigational product) does not meet the definition of an AE. However, to fulfill regulatory requirements any pregnancy should be reported following the SAE process to collect data on the outcome for both mother and fetus.

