10.2. Populations for Analyses

For purposes of analysis of Study JAIM, the following populations are defined:

Population	Description
Modified intent to treat (mITT) Population	All patients who receive at least 1 dose of investigational product in Study JAIM will be included in the mITT population.
Safety Population	The safety population for JAIM is defined as all patients who receive at least 1 dose of investigational product in Study JAIM and who did not discontinue from the study for the reason 'Lost to Follow-up' at the first postbaseline visit.

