- removed the content of Section 7, Unblinding Plan, by referring to a separate unblinding plan
- updated the Anatomical-Therapeutic Chemical (ATC) classification codes and medical review process of prohibited medication in Appendix 1
- added column "Included in Interim 1 Analysis/Derivation" and updated a few categories of patient characteristics in Appendix 2
- added analysis plan for China patients in Appendix 3, and
- made other minor typographical corrections and clarifications not affecting content.

Statistical Analysis Plan Version 4 was approved prior to the database lock/unblinding of the second pivotal originating study JAHZ and prior to the JAIM first interim database lock and unblinding. The key changes include:

- Removed JAHZ **PPD** from the modified intent-to-treat (mITT) population and safety population due to confirmed misconduct that is likely to have significant impact on reliability and robustness of data at this particular site.

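### The JAIM-alone safety population leaves out dosed patients who are lost to follow-up at Week 4, so events already recorded for them leave the safety summaries

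*SAP*

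**What the plan says.** Protocol 10.2 builds the safety population from two conditions. The first is dosing: "The safety population for JAIM is defined as all patients who receive at least 1 dose of investigational product in Study JAIM". The second looks forward from dosing and keeps only those "who did not discontinue from the study for the reason 'Lost to Follow-up' at the first postbaseline visit". The protocol synopsis gives the same rule and adds that all safety data are analysed on this population. SAP Table JAIM.6.2 repeats the rule for analyses of JAIM alone, in the words "and who did not discontinue from the study for the reason 'Lost to Follow-up' at the first postbaseline visit", and the China safety population in SAP Appendix 3 repeats it again. In the Schedule of Activities the first postbaseline visit is Visit 2, at Week 4 (Day 29 ± 4).

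The mITT population in both documents requires only one dose and has no lost-to-follow-up condition.

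On data collection, Protocol 9.2.1 states: "All AEs occurring after signing the ICF are recorded in the eCRF and assessed for serious criteria". Sites must notify SAEs within 24 hours of becoming aware of them.

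A second exclusion stands beside this one. SAP 6.2 says of one site with confirmed misconduct that "the patients from this site will be excluded from the modified intent to treat (mITT) population and safety population".

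**The concern.** A safety population is normally fixed by exposure alone, so that nothing that happens after the first dose can decide whose events are counted. Here the recorded reason for leaving, known only some weeks after dosing, decides it. Patients can be lost for reasons connected with an event, and nothing limits the exclusion to patients with no information after the first dose.

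Safety and tolerability is the primary objective, and permanent discontinuation is one of its endpoints. Protocol 10.3.4 also asks for JAIM-specific summaries of SAEs and of early permanent discontinuation of study drug. On the safety population, a patient lost at Week 4 is removed from the discontinuation count by construction. SAP 6.7 summarises treatment and study disposition on mITT, which keeps that patient, so two tables in the same report could give different counts.

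**Working it through.** **Trace of one patient.** Suppose a patient takes the first JAIM dose on Day 1, has an SAE that the site reports on Day 10, never returns, and is recorded as lost to follow-up at Visit 2.

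| Question | Source | Answer |
|---|---|---|
| Is the event on record? | Protocol 9.2.1 | Yes |
| Does it fall in the safety postbaseline period? | SAP Table JAIM.6.5: from first JAIM dose to the earliest of 30 days after last dose, disposition date or cut-off | Yes |
| Is it a TEAE? | SAP 6.14.1 | The onset condition is met. The upper limit is worded as the last visit date, which is unclear for someone with no visit after Visit 1 |
| Is the patient in mITT? | SAP Table JAIM.6.2 | Yes. SAP 6.4.2.2 counts a patient with no postbaseline observation as a non-responder in the first interval |
| Is the patient in the safety population? | SAP Table JAIM.6.2 | No |
| Is there an all-dosed safety table? | SAP 6.14 | None is planned |
| Does another output show the event? | SAP 6.7 | The all-patient listing there covers disposition, not AEs |
| Do the death, SAE and discontinuation listings show it? | SAP Table JAIM.6.6 | No population is stated, so it cannot be told |

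**Planned size.** Protocol 10.1 gives approximately 1100 patients from 80% completion and 90% roll-over. The originating total is not given, so the figure cannot be reproduced forward; working back, 1100 / (0.80 × 0.90) = 1528. The point does not depend on this. Below, 1100 stands in for the number dosed.

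**Scale of the loss.** The fraction lost at Week 4 is not in the documents. I assume 0.25% to 1%, with 0.1% and 2% as outer values. Exposure is taken to the end of the Week 4 window, Day 33. The rate is the 3.0 serious infections per 100 patient-years that Protocol 3.3 quotes from the rheumatoid arthritis programme, used for scale only.

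Patients = fraction × 1100. Patient-years = patients × 33 / 365.25. Expected serious infections = patient-years × 0.030.

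| Assumed fraction | Patients | Patient-years | Expected serious infections |
|---|---|---|---|
| 0.1% | 1.1 | 0.10 | 0.003 |
| 0.25% | 2.75 (about 3) | 0.25 | 0.007 |
| 1% | 11 | 0.99 | 0.030 |
| 2% | 22 | 1.99 | 0.060 |

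**Effect on a percentage.** Assume 10% of the retained patients have an SAE. With k patients dropped, the all-dosed percentage lies between 0.10 × (1100 − k) / 1100 (none of them had one) and [0.10 × (1100 − k) + k] / 1100 (all did).

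- k = 3: 109.7 / 1100 = 9.97% to 112.7 / 1100 = 10.25%.
- k = 11: 108.9 / 1100 = 9.90% to 119.9 / 1100 = 10.90%.

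**The excluded site.** Its size is not given. Assuming 2 to 30 patients followed for 1 to 3 years, exposure is 2 × 1 = 2 to 30 × 1092 / 365.25 = 89.7 patient-years. At the same rate that is 0.06 to 2.69 expected serious infections. Most of this range lies well above the loss from the lost-to-follow-up rule, which is why a listing is worth having even where the exclusion is sound.

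**The case against.** The best case for the plan runs as follows.

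- **A patient with no data after the first dose dilutes the tables.** Such a patient enters the denominator as event-free. This stands as a possible rationale, although neither document gives one. It would justify leaving out patients with no post-dose information; the rule as written also leaves out those who have some.
- **The overlap of a reported SAE and loss to follow-up is rare.** Protocol 8.3 requires repeated missed visits and failed contact, and Protocol 9.2 has the investigator follow serious AEs until they resolve or stabilise. This stands, and it agrees with the small numbers above.
- **These patients are not invisible.** Disposition is summarised on mITT, the sponsor reviews all deaths and SAE reports, suspected VTEs are adjudicated, and a DMC oversees the programme. This also stands, but none of it puts a recorded event back into the JAIM-alone summaries.

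A reader might also infer more than the documents support.

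- **That the site exclusion is the same fault.** It is not. The stated reason is misconduct "likely to have significant impact on reliability and robustness of data at this particular site", a site-level judgement and not a patient's outcome after dosing. SAP Section 3 records that the version introducing it was approved "prior to the JAIM first interim database lock and unblinding".
- **That the primary safety result or the AESI counts are affected.** Protocol 10.3.4 places the primary endpoints in the integrated safety analyses. SAP 6.14.5 does the same for special safety topics, leaving only infections for JAIM alone. Protocol 10.3.1 lets populations differ between integrated and JAIM-alone analyses. The integrated plan is not available, so its population cannot be checked.
- **That a previous year of exposure is lost for continuing patients.** JAIM-alone safety counts from the first JAIM dose, so about one month per patient is at issue.
- **That percentages are biased downwards.** Event counts can only fall, but the percentages can move either way, as the bounds show.

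**Conclusion.** The point holds for JAIM-alone safety outputs. Four places in the two documents make membership of the safety population depend on an outcome after dosing, and AEs or SAEs already on record for those patients, with the discontinuation itself, leave the summaries run on it. The mITT population keeps the same patients, so for the primary objective the plan uses the narrower set.

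The expected size is small: about 3 to 11 patients and at most about one patient-year in total, if 0.25% to 1% of 1100 are lost at Week 4. That fraction is my assumption. Pooled percentages would move by a fraction of a point in most cases; what matters is an individual serious event. This is a cheap improvement to make, not a threat to the trial's conclusions. The site exclusion is not an error; what is missing there is a listing of events in patients who were exposed to study drug.

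**What to change.** 1. In the protocol synopsis, Protocol 10.2, SAP Table JAIM.6.2 and SAP Appendix 3, define the JAIM safety population by dosing alone (one or more doses of JAIM study drug) and delete the lost-to-follow-up condition. SAP Table JAIM.6.2 keeps its site exclusion.
2. For patients with no later visit, count exposure to last known contact. Align the TEAE end date in SAP 6.14.1 with Table JAIM.6.5, so that an event reported between visits is not lost a second time.
3. State the population for each listing in SAP Table JAIM.6.6.
4. Keep the misconduct site out of the summary tables, and add a by-patient listing of its deaths, SAEs and AEs leading to discontinuation, marked as coming from a site with unreliable data.

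The cost is four edits to a definition, a clarification of dates and one extra listing. Protocol 10.3.1 requires an amendment only if a principal feature changes, and otherwise a justified description in the study report; the sponsor has to judge which applies. The downside is that a few patients with little exposure enter the denominators and may slightly lower crude percentages.

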### 6.3. Definition of Baseline and Postbaseline Periods

For efficacy analyses, *baseline* for patients receiving active treatment (baricitinib 2-mg and 4-mg) in originating studies (JAHZ and JAIA) is defined as the last nonmissing measurement taken in the originating studies, prior to starting study medication. *Baseline* for patients receiving placebo in originating studies is defined as the last nonmissing assessment prior to the first dose of active study drug given in Study JAIM Visit 1 (Week 0). Any assessment collected after the JAIM Visit 1 dose through the date of Visit 11 or the early discontinuation visit is defined as *postbaseline* for the Treatment Period.

Protocol-defined visit windows are defined as  $\pm 4$  days for Visit 2 (Week 4),  $\pm 7$  days for Visit 3 (Week 12),  $\pm 10$  days from Visit 4 (Week 24) until Visit 7 (Week 60), and  $\pm 14$  days from Visit 8 (Week 84) until Visit 11 (Week 156). If there are data within the protocol-defined window, those data will be used in by-visit analyses. If a protocol-defined visit is missing, then the nearest unscheduled visit data that exist will be mapped to that visit and included in by-visit analyses.

For safety analyses, baseline is defined as the last nonmissing scheduled (planned) measurement prior to the first dose of baricitinib administration in Study JAIM for continuous measures by-

visit analyses and all nonmissing measurements prior to the first dose of the study drug administration (baricitinib) in Study JAIM for all other analyses.

Postbaseline measures for the safety analyses are defined as the nonmissing scheduled (planned) measurements after the first dose of baricitinib administration in Study JAIM for continuous measures by-visit analyses and all nonmissing measurements after the first dose of the study drug administration (baricitinib) in Study JAIM for all other analyses.

In general, when the baseline measurement is collected on the same day (where time is not collected) as the first dose date, this measurement will be used as the baseline value for efficacy and safety except adverse events (AEs).

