### **6.4.2. Handling of Dropouts or Missing Data**

Due to the long duration of JAIME, missing data that are imputed will be carried forward for the visit interval at Week 48, Week 108, and Week 156. Discontinued patients will not be included for evaluation in intervals subsequent to their discontinuation from the study. The following visit intervals are defined for NRI method and mLOCF method:

- Visit 6 (Week 48) [ $>$  Visit 1 (Week 0) and  $\leq$  Visit 6 (Week 48)]
- Visit 9 (Week 108) [ $>$  Visit 6 (Week 48) and  $\leq$  Visit 9 (Week 108)]
- Visit 11 (Week 156) [ $>$  Visit 9 (Week 108)]

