#### **6.4.2.1. As-Observed Analysis**

The “as-observed” strategy is used in so-called “observed cases” or “completers” analysis, ubiquitous in the literature, but is not one of the recommended strategies in the ICH E9(R1). For this analysis, only data from completers at the visit are relevant, and therefore the analysis does not need to deal with missing data. This estimand is based on the subset of patients who would complete treatment through Visit X if assigned to it. Therefore, this estimand is conditional and targets the effect of treatment conditional on completion of treatment through the time point of interest. Because the estimand is defined for a subpopulation conditional on an intercurrent event, it is not causal. Summaries based on observed data at each postbaseline visit will be provided.

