### 6.4.2.3. Mixed Model for Repeated Measures

For continuous variables, an MMRM analysis with a missing at random assumption for handling missing data will be performed. This likelihood-based analysis takes into account both missingness of data and the correlation of the repeated measurements.

The MMRM method may be justified when the estimand of interest uses the hypothetical strategy (EMA2020) for handling intercurrent events. In this strategy, the scientific question of interest is to assess the effect of study treatment in a hypothetical trial where all patients have complete data and continue to take study treatment as directed without dropping out of the study.

For patients who have prohibited medication use any time after baseline, any observed data after the date of the prohibited medication use will be excluded from the MMRM analysis. The earliest date of prohibited medications will be used for censoring.

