**Table JAIM.6.4. Description of Efficacy/Health Outcomes Analyses**

Measure	Variable	Analysis Method	Population	Key Time Point(s) a
SRI-4	Proportion of patients achieving SRI-4 response	Descriptive analysis with observed and NRI	mITT, patients with SLEDAI-2K score of $\geq 4$ at baseline	Week 156 visit
SRI-x (where x is 5, 6, 7, 8)	Proportion of patients achieving SRI-x response	Descriptive analysis with observed and NRI	mITT, patients with SLEDAI-2K score of $\geq x$ at baseline	Week 156 visit
SLEDAI-2K	Change from baseline in mean total SLEDAI-2K through Week 156	MMRM	mITT	Week 156 visit
	Proportion of patients achieving reduction of $\geq 4$ points from baseline	Descriptive analysis with observed and NRI	mITT, patients with SLEDAI-2K score $\geq 4$ at baseline	Week 156 visit
	Proportion of patients with improvement in each SLEDAI-2K individual organ systems vs baseline	Descriptive analysis with observed and NRI	mITT, patients with SLEDAI-2K score $> 0$ within the organ domain at baseline	Week 156 visit
	Proportion of patients with worsening in each SLEDAI-2K individual organ system vs baseline	Descriptive analysis with observed and NRI	mITT, patients with at least 1 SLEDAI-2K item = 0 in the organ domain at baseline	Week 156 visit
BILAG	Proportion of patients with no new BILAG A and no more than 1 new BILAG B disease activity score (compared with baseline)	Descriptive analysis with observed and NRI	mITT	Week 156 visit
	Proportion of patients with improvement in each BILAG individual organ system vs baseline	Descriptive analysis with observed and NRI	mITT, patients with BILAG A or B in the organ domain at baseline	Week 156 visit
	Proportion of patients with worsening in each BILAG individual organ system vs baseline	Descriptive analysis with observed and NRI	mITT, patients without BILAG A in the organ domain at baseline	Week 156 visit
PGA	Proportion of patients with no worsening in PGA (compared with baseline)	Descriptive analysis with observed and NRI	mITT	Week 156 visit
	Change from baseline in PGA score over time through Week 156	MMRM	mITT	Week 156 visit
BICLA	Proportion of patients achieving BICLA response	Descriptive analysis with observed and NRI	mITT	Week 156 visit
28 Tender/Swollen Joint Count	Change from baseline in tender joint count	MMRM	mITT	Week 156 visit
	Change from baseline in swollen joint count	MMRM	mITT	Week 156 visit

Measure	Variable	Analysis Method	Population	Key Time Point(s) a

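### SAP 6.3 fills a missing scheduled visit with the nearest unscheduled record without any distance, tie or reuse limit, so efficacy values from months away can be reported at visits such as Week 156

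*SAP*

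**What the plan says.** SAP 6.3 repeats the visit windows of the Schedule of Activities, which widen to 14 days either side from Week 84 to Week 156. Data inside the window are used first. If the visit is missing, "the nearest unscheduled visit data that exist will be mapped to that visit and included in by-visit analyses". The only time limit in that section is its definition of postbaseline efficacy data, which opens "Any assessment collected after the JAIM Visit 1 dose through the date of Visit 11 or the early discontinuation visit is defined as".

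Four other parts of the SAP bear on the rule:
- SAP 6.4.2: "Discontinued patients will not be included for evaluation in intervals subsequent to their discontinuation from the study". The intervals end at Weeks 48, 108 and 156 and are introduced with "The following visit intervals are defined for NRI method and mLOCF method".
- SAP 6.4.2.1, on the as-observed analysis: "only data from completers at the visit are relevant".
- SAP 6.4.2.3, on the MMRM, gives one exclusion: "any observed data after the date of the prohibited medication use will be excluded from the MMRM analysis".
- SAP Table JAIM.6.4 gives "Week 156 visit" as the key time point for nearly every efficacy and health-outcome endpoint. Its footnote adds that measures collected at several visits are analysed at each of them.

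**The concern.** A by-visit result should describe patients at about that visit. This rule takes whatever unscheduled record is closest, however far away, and labels it with the missing visit. It does not say what to do when two records are equally close, or whether one record may stand in for two or more missing visits. Two programmers could build different Week 156 datasets from the same text, and both would be following it.

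The effect is sharpest in the MMRM. SAP 6.4.2.3 relies on the likelihood to deal with missing visits under a missing-at-random assumption. A mapped value removes the gap and puts an observation from another time in its place. The model then treats it as a genuine measurement at the target visit, and it enters the least squares mean and the within-group test against zero described in SAP 6.1.

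**Working it through.** **Inputs.** Scheduled days are from Protocol Table JAIM.1. Windows and the postbaseline period are from SAP 6.3. The visit intervals are from SAP 6.4.2. The 36-day recency limit is from SAP Table JAIM.6.3.

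**1. Reproduce the schedule.** Study day = 7 × week + 1. For Week 156, 7 × 156 + 1 = 1093, as stated. All ten postbaseline days reproduce (29, 85, 169, 253, 337, 421, 589, 757, 925, 1093), and the SAP windows match the protocol's. The Week 132 window is Days 911 to 939 and the Week 156 window is Days 1079 to 1107. Between them, 1078 − 940 + 1 = 139 days belong to no window.

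**2. Distances allowed at Week 156.** Suppose Visit 11 is missing. Distance = 1093 − day of the nearest unscheduled record.

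| Unscheduled record | Distance from Day 1093 |
|---|---|
| Day 1078 (last day before the window) | 15 days |
| Day 940 (first day after the Week 132 window) | 153 days |
| Day 758 (day after the Week 108 target) | 335 days |
| Day 337 (Week 48 target) | 756 days |
| Day 2 (day after the first dose) | 1,091 days |

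Each row qualifies if it is the patient's closest unscheduled record. The bottom rows need a patient with no later unscheduled record.

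**3. Reuse and ties.** A record on Day 1009 is 1009 − 925 = 84 days from Week 132 and 1093 − 1009 = 84 days from Week 156. If both visits are missing and it is the only unscheduled record, the text assigns it to both. If two records lie equally far from one visit, the text does not choose.

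**4. Which analyses are exposed.**
- *MMRM.* SAP 6.4.2.3 has no distance limit and no discontinuation limit. As an assumed example, take a patient who stops after the Week 36 visit and whose only unscheduled record is at Week 30 (7 × 30 + 1 = Day 211). Read literally, that record is nearest to Weeks 48, 60, 84, 108, 132 and 156. It would fill all six, at distances from 337 − 211 = 126 days to 1093 − 211 = 882 days.
- *NRI.* SAP 6.4.2.2 makes patients non-responders for discontinuation, prohibited medication or having no postbaseline observation. A continuing patient who merely misses a visit meets none of these, so a mapped record can decide response.
- *As-observed.* A mapped record can make a continuing patient appear observed at the missed visit.
- *mLOCF.* This is used for the SLICC/ACR damage index. SAP 6.4.2.4 fills a missed visit only when no value is observed or already supplied by other means. Mapping can therefore come first, and an older unscheduled record could displace a later scheduled one.
- *Safety.* Continuous by-visit analyses use planned measurements only (SAP 6.3 and Table JAIM.6.5), so the rule does not reach them.

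**5. Does another rule cap the distance?** The 36-day limits in Table JAIM.6.3 govern carrying forward instrument data, several of them only when the visit took place. They do not govern mapping of a missing visit. No other section sets a limit.

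**6. Effect of a cap.** A midpoint bound for Week 156 is (925 + 1093)/2 = Day 1009, at most 84 days early. The 36-day limit gives 1093 − 36 = Day 1057. The present text allows 1,091 days.

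**The case against.** The strongest reply is that Week 156 is the last treatment visit, so a patient without it has usually discontinued, and discontinuation is already handled. NRI makes the patient a non-responder for that interval and drops later ones, mLOCF carries a value within that interval only, and the as-observed analysis is restricted to completers at the visit. This stands for those three analyses. It does not reach the MMRM, or a continuing patient who misses a visit. If the interval sentence in SAP 6.4.2 were read to cover the MMRM too, the example of the patient who stops after Week 36 would shrink to Week 48, but the SAP defines the intervals only for NRI and mLOCF.

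Three stronger readings are tempting and are not supported:
- A reader might infer that records collected after discontinuation can be pulled in, or that the mapping rule overrides the interval rule. SAP 6.3 ends efficacy data at Visit 11 or the early discontinuation visit, and nothing in it overrides SAP 6.4.2. What remains is an earlier record mapped forward.
- A reader might infer a known direction of bias, on the view that unscheduled visits happen when patients are unwell. The documents do not say why they happen, and SAP 6.15 foresees missed and out-of-window visits caused by COVID-19 logistics.
- A reader might infer that every MMRM endpoint is affected alike. Prednisone dose comes from daily dosing records, taken on the day before the visit date (SAP 6.10.1), so it does not depend on an unscheduled assessment in the same way.

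It is also fair that efficacy is not the primary outcome (SAP 6.11.2) and that no between-group inference is planned unless otherwise stated (SAP 6.1). That limits the consequence. It does not make the rule sound.

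**Conclusion.** The point holds for efficacy and health-outcome by-visit analyses. The stated rule permits a value to be reported months from its true date, and in the extreme 1,091 days from it, with no tie rule and no bar on reuse. The main exposure is the MMRM, followed by observed, NRI and mLOCF results for continuing patients who miss a visit. Discontinued patients are largely covered outside the MMRM, and continuous by-visit safety analyses are not affected.

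These distances are what the text allows, not what will occur. The number of affected records depends on how many visits are missed and how many unscheduled efficacy assessments exist, and the documents give neither. The conclusion assumes that the rule is programmed as written. An unwritten cap applied by the analyst would avoid the problem but would not be pre-specified. The change should be made, but the primary safety objective does not turn on it.

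**What to change.** Amend SAP 6.3 for efficacy and health-outcome by-visit analyses:
- Map an unscheduled record only if it falls in a pre-stated analysis window around the target day. Two candidates are midpoints between adjacent scheduled visits (at most 84 days either side after Week 60) and the 36-day limit that the SAP already uses for instrument data. The choice is a judgement; stating one is what matters.
- Use each record for one visit only, and state a tie rule.
- Do not map to visits scheduled after treatment discontinuation, and say that this includes the MMRM.
- Otherwise leave the visit missing for the MMRM, NRI and mLOCF rules.
- Say whether a scheduled visit held outside its window counts as missing, and whether an early termination visit counts as unscheduled. SAP 6.4.2.4 lists unscheduled and early termination visits separately.

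The cost is a few sentences and a window table, with no new data collection. The downside is that some visits now filled become missing, more of them under the 36-day limit than under midpoints.
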